8.3.5 Per Protocol (PP) Set Immunogenicity Set

All subjects in the FAS Immunogenicity who:

- Correctly receive the booster dose (only for analysis of boostability).
- Have no protocol deviations leading to exclusion (see [section 8.3.8, Protocol Deviations](#)) as defined prior to analysis.
- Are not excluded due to other reasons defined prior to analysis (see [section 8.3.8, Protocol Deviations](#))

Examples for subjects excluded due to other reasons than protocol deviations are:

Subjects who withdrew informed consent.

Analogously to FAS, inclusion of subjects in the PPS is defined by objective.

Further details on Per Protocol Immunogenicity sets are provided in the statistical analysis plan.

8.3.6 Other Analysis Sets

Not applicable.

8.3.7 Subgroups

Not applicable.

8.3.8 Protocol Deviations

A protocol deviation is any change, divergence, or departure from the study design or procedures of a study protocol. A protocol deviation may be a reason to remove data from an analysis set at the time of analysis. CSR-reportable protocol deviations will be defined as exclusionary from the analysis according to protocol objectives and endpoints, which will be specified in the statistical analysis plan. In some cases exclusion of data may be due to a reason other than a protocol deviation, e.g. early termination.

8.4 Statistical Analysis Plan

8.4.1 Analysis of Demographic and Baseline Characteristics

Descriptive statistics (mean, standard deviation, median, minimum and maximum) for age, height and weight, body mass index (BMI) at enrolment will be calculated overall and by vaccine group.

Distributions of subjects by sex and ethnic origin will be summarized overall and by vaccine group.

8.4.2 Analysis of Primary Objective(s)

8.4.2.1 Analysis of Primary Safety Objective

Number and percentages of SAEs will be summarized only for subjects receiving a booster dose by the vaccination regimen received in the parent study V49_23 and overall.

8.4.2.1.1 Analysis of Extent of Exposure

Not applicable.

8.4.2.1.2 Analysis of Solicited Local, Systemic and Other Adverse Events

Not applicable.

8.4.2.1.3 Analysis of Unsolicited Adverse Events (Amended 25 February 2019)

This analysis applies to all **SAEs** occurring during the study, judged either as probably related, possibly related, or not related to vaccination by the investigator, recorded in AE CRF, with a start date on or after the date of booster dose. SAE starting prior to booster dose will not be recorded. The original verbatim terms used by investigators to identify adverse events in the CRFs will be mapped to preferred terms using the MedDRA

dictionary. The serious adverse events will then be grouped by MedDRA preferred terms into frequency tables according to system organ class.

All reported serious adverse events, as well as serious adverse events judged by the investigator as at least possibly related to study vaccine, will be summarized according to system organ class and preferred term within system organ class. When a serious adverse event occurs more than once for a subject, the maximal severity and strongest relationship to the vaccine group will be counted.

Separate summaries will be produced for the following categories:

- Serious adverse events.
- Serious adverse events that are possibly or probably related to vaccine.
- Serious Adverse event leading to withdrawal.
- Deaths

Data listings of all serious adverse events will be provided by subject. In addition, serious adverse events in the categories above will be provided as listed data.

8.4.2.1.4 Analysis of Safety Laboratory Values

Not applicable.

8.4.2.2 Analysis of Primary Efficacy Objective(s)

Not applicable.

8.4.2.2.1 Statistical Hypotheses

Not applicable.

8.4.2.2.2 Analysis Sets

Not applicable.

8.4.2.2.3 Statistical Methods

Not applicable.

8.4.2.3 Analysis of Primary Immunogenicity Objective(s)

8.4.2.3.1 Statistical Hypotheses

Not applicable.

8.4.2.3.2 Analysis Sets (Amended 25 February 2019)

All Enrolled Set.

FAS-1: Booster Immunogenicity Analysis Set.

Analyses on PPS will be conducted only if more than 10% of subjects have CSR-reportable **protocol** deviations (by objective).

For analysis sets definition see [section 8.3](#).

8.4.2.3.3 Statistical Methods (Amended 25 February 2019)

Time to first RVNA concentrations <0.5 IU/mL.

For each subject time to first RVNA concentrations <0.5 IU/mL will be calculated. Kaplan-Meier (**KM**) estimate of the survival function, along with 95% CIs, will be estimated and displayed per each vaccination regimen. Standard errors of the KM estimates will be based on the Greenwood's method; 25th and 75th percentile and median survival will be provided if estimable.

In this setting, the event/failure will be represented by the administration of the booster dose. Subjects without event will be regarded as right-censored data. Dropouts will be considered as non-informative data and judged as Missing Completely At Random (MCAR) as an association between the missingness mechanism and the vaccine efficacy or safety is implausible.

Group comparisons for first occurrences of a boost will be performed using the unadjusted Cox proportional hazard regression model (only treatment effect will be included). Ties will be handled with the exact method as it assumes that there is a true but unknown ordering for the tied event times. Hazard **Ratios** (HR) and 95% CIs will be computed. In case of not estimable HRs, alternative methods will be attempted.

It is expected that no or very few subjects will need more than one booster dose during the study conduct. Nevertheless, a contingency analysis will be performed counting the frequency of subjects who receive 0 booster, 1 booster, 2 boosters, 3 or more boosters.

If a relevant number of subjects will need more than one booster dose during the study conduct, the Andersen-Gill method will be used to analyze multiple events data.

Geometric Mean Ratio (GMR).

RVNA GMCs will be based on the logarithmically transformed (base10) values.

For subjects receiving a booster dose, analysis of boostability will be conducted 7 days and at also approximately 6 months after administration of the booster dose by providing GMRs and associated 95% CIs, considering the antibody value at the booster visit as baseline (denominator) and the antibody concentration at 7 days (and approximately at 6 months) after booster as the numerator.

Additionally, all boosted subjects will be pooled together and their RVNA concentrations analyzed using an ANOVA model that includes vaccine regimen group and time in study of the booster dose as factors in the model along with their interaction. For this analysis, values, as measured at day 7 (and also approximately at 6 months) after booster dose, will be used.

Percentages of subjects with RVNA concentrations ≥ 0.5 IU/mL, as measured by RFFIT assay at 7 days after the booster dose and at subsequent scheduled clinical visit.

Percentages and 95% CIs will be presented by vaccine regimen.

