3.9 End of Study

Most clinical trials intended to support the immunogenicity and safety of an Investigational Product proceed to full completion of planned sample size accrual.

Evaluation of the primary immunogenicity objectives requires the testing of biological samples from the study subjects, which can only be completed after all samples are collected. The last samples for the analysis of the primary objectives will be taken at Visit 8. For the purpose of this protocol, end of study is defined as the completion of the testing of such biological samples, to be achieved no later than 8 months after collection of the last biological sample at the Scheduled Clinic Visit 8 (Year 10).

Should a subject have RVNA concentrations below 0.5 IU/mL at blood draw performed at the final Scheduled Clinic Visit (Year 10), the subject will be invited to receive a booster dose of the rabies vaccine outside the study following standard clinical practice and there will be no further analyses performed on this additional vaccination.

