8. GENERAL ISSUES FOR STATISTICAL ANALYSES

8.1. Adjustment for Covariates

Cox proportional hazards regression model – Time to first RVNA <0.5IU/mL

The hazard ratio (HR) from the Cox ([Andersen](#), 1982) proportional hazards regression model will be used as a treatment effect measure for time to event endpoints.

Group comparisons for first occurrences of a booster (i.e., RVNA concentration <0.5 IU/mL) will be performed using an adjusted Cox proportional hazard regression model with effect for treatment and center. Ties will be handled with the exact method as it assumes that there is a true but unknown ordering for the tied event times.

Analysis of Variance (ANOVA) – Analysis of boostability.

For subjects who will receive rabies vaccine booster the log-transformed antibody concentration at day 7 will be analyzed using an Analysis of Variance (ANOVA) which includes treatment (vaccine received at time of parent study V49_23) and center. Summary tables will show adjusted GMCs and GMR for each treatment and adjusted ratios of GMCs between vaccine groups.

Mixed model for repeated measures – Analysis of persistence

Log-transformed antibody titers as collected at annual Scheduled Visits (from Visit 1 to Visit 7) will be analyzed using a mixed model for repeated measures within subject, including time and treatment as independent variables, their interaction and a random intercept with an unstructured covariance matrix.

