8.2. Handling of Dropouts, Missing Data

Time to event analysis:

The Cox proportional hazards regression model analysis will be based on methods for right-censored data ([Lindsey](#), 1998).

In this setting, the event/failure will be represented by having a RVNA concentration <0.5 IU/mL (see section [8.8](#)). Subjects without event (with missing blood draw, or lost to follow up or early terminated) will be regarded as right-censored data.

GMC and percentage analysis - boostability:

To evaluate the booster response in terms of Geometric Mean Concentration (GMC), Geometric Mean Ratio (GMR) and percentage of subjects with RVNA concentration ≥ 0.5 IU/mL; missing data will be not included in the analysis.

GMC and percentages of subjects with RVNA concentrations ≥ 0.5 IU/mL

To evaluate the long-term (up to approx.10 years) immunogenicity in subjects who received a primary series of accelerated or conventional rabies PrEP in the parent study (V49_23) in terms of GMC and percentage of subjects with RVNA concentration ≥ 0.5 IU/mL; missing data as such will be not included in the analysis. If a subject receives a rabies vaccine booster dose, the RVNA value after booster will be set to half of quantification level from that moment onward. This because the exposure to a booster dose during the trial introduces a bias, as the RVNA concentrations will reflect the booster response and not the long-term persistence after the primary series (i.e., vaccination received at time of parent study).

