If one of the followings occur, subject will be censored (censor=0) and time to the last data available strictly before the event will be included in the survival analysis:

- Subject is lost to follow up
- Subject withdraws consent
- RVNA concentration not available for last visit (last visit could differ from the final visit)
- Subject receives booster (study vaccine or another rabies vaccine) but RVNA concentration ≥ 0.5 or unknown
- Subject performs final visit (i.e., study termination visit) and RVNA concentration is ≥ 0.5 IU/mL (for the purpose of the IA, if visit 4 is completed by the subject he will be considered as a censored value at the time of visit 4)

The subjects will be considered as censored if any of the following event occurs before the subject's antibody titer level goes beyond the level of 0.5IU/mL:

- All further blood draw results are missing

Censor variable will be set to 0 if any of the case above occurs. If the subject's antibody level titer goes beyond 0.5 IU/mL censoring values will be set to 0 at the time of the 1st antibody titer level below 0.5 IU/mL.

Point Variable describes the order of RVNA concentration observed. It will be POINT=5 if a subject receives booster between V49_23 END (last visit date) and V49_23E1 START (first visit date).

Immunogenicity

Values below the limit of quantification (recorded as “< LQ”) will be set to half that limit (i.e., LQ/2]).

Geometric Mean Concentration

The GMC will be calculated using the following formula:

$$10^{\left[\frac{\sum_{i=1}^n \log_{10}(t_i)}{n} \right]}$$

where t_1, t_2, \dots, t_n are n observed immunogenicity titers/concentrations.

Geometric Mean Ratio

Geometric mean ratios (GMRs) measure the changes in immunogenicity concentrations *within* subjects.

The GMR will be calculated using the following formula:

$$10^{\left[\frac{\sum_{i=1}^n \log_{10}\left(\frac{v_{ij}}{v_{ik}}\right)}{n} \right]} = 10^{\left[\frac{\sum_{i=1}^n \log_{10}(v_{ij}) - \log_{10}(v_{ik})}{n} \right]}$$

where, for n subjects, v_{ij} and v_{ik} are observed immunogenicity titers/concentrations for subject i at time-points j and k , $j \neq k$.

Imputation of RVNA concentration in subjects receiving a booster

Once a subject receives a rabies vaccine booster dose (i.e. RVNA<0.5) he/she will be treated as follows:

Time to event analysis:

Censor=1 for the time-point in which RVNA is observed being below 0.5 IU/mL

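### Protocol 8.4.2.3.3 makes giving the booster the primary time-to-event failure, against its own endpoint and the SAP's event of first RVNA <0.5 IU/mL; one SAP 8.8 sentence also reverses the event indicator

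*Protocol*

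**What the plan says.** **Protocol.** Section 8.1.1.3 lists time to first RVNA <0.5 IU/mL as a primary endpoint. Section 8.4.2.3.3 begins in agreement: "For each subject time to first RVNA concentrations <0.5 IU/mL will be calculated". It then states that "the event/failure will be represented by the administration of the booster dose", describes the group comparison in terms of first boosts, and plans a recurrent-events method if many subjects need repeat boosters. The comparison "will be performed using the unadjusted Cox proportional hazard regression model".

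**SAP, event.** Section 8.2 states that "the event/failure will be represented by having a RVNA concentration <0.5 IU/mL". Section 8.8 defines the indicator as 0 for censored and 1 for event, gives RVNA <0.5 the value 1, and codes it that way in SAS. Section 11.2 names the same event. Section 8.1 words the comparison as "Group comparisons for first occurrences of a booster (i.e., RVNA concentration <0.5 IU/mL", so the parenthesis treats the two events as one.

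**SAP, censoring.** Section 8.8 also says that once the titre passes 0.5 IU/mL "censoring values will be set to 0 at the time of the 1st antibody titer level below 0.5 IU/mL". Later in the same section, the indicator is to be 1 at the time-point where RVNA is seen below 0.5 IU/mL.

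**SAP, model.** The comparison "will be performed using an adjusted Cox proportional hazard regression model with effect for treatment and center". Sections 8.3 and 11.2 also include centre.

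The SAP's history of changes mentions revised survival-analysis information, but neither declares a departure from the protocol's event or model nor says which document governs.

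**The concern.** Protocol 8.4.2.3.3 names one event for its endpoint and uses another for its analysis. If the booster sentence were followed, falls in antibody would be missed or dated late, and some boosters that do not reflect a fall could count as failures. Kaplan-Meier quartiles and medians are planned outputs. The interim report may go to a Health Authority if results support a booster at a given time after the primary regimen, so a shift in event times bears on the question that the report may be used to answer.

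The SAP 8.8 sentence is a second fault. Taken literally, it codes every observed fall as censored.

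The study is open-label, so the event and the model should be fixed in writing and not left to choice at analysis.

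**Working it through.** **1. Are the two event rules equivalent?**

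| Situation | SAP rule (RVNA <0.5) | Protocol sentence (booster given) |
|---|---|---|
| First low value at Year 10 | Event | Never an in-study event: under Protocol 3.9 "the subject will be invited to receive a booster dose of the rabies vaccine outside the study following standard clinical practice" |
| Low value, no booster (pre-booster exclusions in Protocol 4.2; pregnancy or related SAE in 3.8; SAP Table 4 has a code for it) | Event | No event |
| Low value, Ad hoc visit missed | Event at the draw | Delayed, not necessarily lost: Protocol 3.8 allows a redraw and a later booster |
| Low value in the parent study, Day 57 to Day 366 | Event at that visit (SAP 8.8) | No event then; counted only if a booster follows a Year 3 or later draw |
| Booster at RVNA ≥0.5 or unknown | Censored (SAP 8.8); SAP 7.3 removes some of these subjects from the long-term set | Can be an event |
| Low value, boosted as planned | Dated at the planned visit | Dated about 6 to 9 months later (0.5 to 0.75 year) |

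The rules differ in which subjects fail and when.

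**2. Share of falls first seen at Year 10.** The documents give no rate of decline, so a constant annual risk *h* of 2%, 5% or 10% is assumed. With *k* annual periods, the share of first falls in the last one is h(1−h)^(k−1) / [1−(1−h)^k].

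| Falls counted | h = 0.02 | h = 0.05 | h = 0.10 |
|---|---|---|---|
| Visits 1-8 only, one year of risk each (k = 8) | 11.6% | 10.4% | 8.4% |
| Visits 1-8, two years of risk accruing at Visit 1 (k = 9) | 10.2% | 9.0% | 7.0% |
| Ten years of falls (k = 10) | 9.1% | 7.9% | 5.9% |

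Example, k = 10 and h = 0.05: 0.05 × 0.95^9 / (1 − 0.95^10) = 0.0315 / 0.4013 = 7.9%.

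The last row is closer to the SAP analysis, which also counts parent-study data.

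**3. Illustrative simulation.** Neither document has a sample size or event target to reproduce; the number invited is at most 158 + 209 + 211 = 578. The simulation used 369 conventional and 209 accelerated subjects, exponential times to RVNA <0.5, 60 runs per scenario, no dropout and Efron ties. Annual hazards (conventional/accelerated) and the proportion of eligible subjects not boosted are assumptions. No boosters at RVNA ≥0.5 were simulated. Parent-study falls could still be boosted after Year 3.

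| Hazards | Not boosted | Events, SAP rule | Events, booster rule | Fewer | HR, SAP / booster |
|---|---|---|---|---|---|
| 0.02 / 0.04 | 0% | 136.1 | 124.6 | 8% | 2.09 / 2.10 |
| 0.02 / 0.04 | 20% | 136.1 | 99.9 | 27% | 2.07 / 2.02 |
| 0.04 / 0.08 | 0% | 233.0 | 215.0 | 8% | 2.10 / 2.09 |
| 0.04 / 0.08 | 20% | 237.6 | 174.8 | 26% | 2.01 / 1.96 |
| 0.06 / 0.15 | 0% | 329.8 | 309.4 | 6% | 2.49 / 2.48 |
| 0.06 / 0.15 | 20% | 327.1 | 247.4 | 24% | 2.48 / 2.26 |

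Scenarios with 10% not boosted lie between these, at about 16-17% fewer events. When every eligible subject is boosted, the shortfall equals the Year 10 falls within rounding (for example 329.8 − 309.4 = 20.4). About 16 to 51 SAP events fell before Year 3.

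**4. The SAP 8.8 sentence.** With 0 meaning censored, setting the indicator to 0 at the first titre below 0.5 leaves no events and no estimable hazard ratio. The definition, the SAS code and the later rule in the same section all set it to 1.

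**The case against.** The strongest reply is that the intended event is clear. The objective, the listed endpoint and the protocol's own calculation sentence all use RVNA <0.5 IU/mL. So does the SAP in 8.2, in the 8.8 definition and code, in 11.2 and in the parenthesis in 8.1. A programmer following the SAP would code a fall as 1. There is no hypothesis or success criterion, so no formal decision rests on the choice, and the simulated hazard ratio barely moved in most scenarios.

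Most of this stands, and it rules out several stronger readings:

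- A reader might infer that the primary analysis has no usable definition. The SAP has one dominant definition, and its intent is recoverable.
- A reader might infer that the analysis would produce no events. That follows only from one sentence read alone; the SAP's own code produces events.
- A reader might infer that the protocol rule always lengthens apparent persistence. Late dating and lost falls do, but counting boosters at RVNA ≥0.5 or unknown works the other way.
- A reader might infer that the regimen comparison is seriously distorted. The simulation does not show that, although its inputs are assumed.

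The reply does not remove the contradiction. The booster sentence is current protocol text, in a section marked as amended in February 2019, and the surrounding text on first and repeat boosts follows it. The SAP departs from it without saying so.

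**Conclusion.** The protocol's event sentence is wrong for its stated endpoint and conflicts with the SAP's operative definition. The consequence is mainly for event counts and Kaplan-Meier times: Year 10 falls are excluded (about 6-9% of falls over ten years, or 7-12% at Visits 1-8, on assumed annual risks of 2-10%), and boosted falls are dated 0.5 to 0.75 year late. Across the simulated scenarios the booster rule gave about 6-27% fewer events; the upper end rests on an assumed 20% of eligible subjects not being boosted. The largest hazard-ratio gap was 2.48 against 2.26.

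The SAP 8.8 sentence is probably a drafting error, but it contradicts the code it sits beside and should be corrected. The change of Cox model is a separate, undeclared departure; the SAP is consistent within itself on centre adjustment.

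**What to change.** 1. **Protocol 8.4.2.3.3.** Replace the booster event with the first RVNA <0.5 IU/mL at any planned draw in the SAP's time-to-event window (parent-study Day 57 to Day 366 and extension Years 3 to 10), dated at that planned visit, whether or not a booster follows. Limiting it to the extension's Scheduled Clinic Visits would drop the parent-study events. Keep the SAP 8.8 censoring of boosters given at RVNA ≥0.5 or unknown. If the protocol is not amended, record this in the SAP as a declared departure.
2. **SAP 8.8.** Correct the reversed sentence so that the indicator is 1 at the first titre below 0.5 IU/mL. Use one variable name: the derivation calls it CENSOR, the 11.2 code calls it status.
3. **SAP 8.1.** Remove the booster wording from the group-comparison sentence and keep the definition in its parenthesis.
4. **Cox model.** Record the move from the unadjusted model (protocol) to the centre-adjusted one (SAP 8.1, 8.3, 11.2) as a departure. An unadjusted sensitivity analysis is optional.

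The cost is wording, with no new data. Because item 1 restates the primary event, whether a protocol change would count as administrative should be checked against Protocol 13.4; the declared departure in the SAP is the lighter route.

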8.4.3 Analysis of Secondary Objective(s)

Not applicable.

8.4.3.1 Analysis of Secondary Safety Objective(s)

8.4.3.1.1 Analysis of Extent of Exposure

Not applicable.

8.4.3.1.2 Analysis of Solicited Local, Systemic and Other Adverse Events

Not applicable.

8.4.3.1.3 Analysis of Unsolicited Adverse Events

Not applicable.

8.4.3.1.4 Statistical Hypotheses

Not applicable.

8.4.3.1.5 Analysis Sets

Not applicable.

8.4.3.1.6 Statistical Methods

Not applicable.

8.4.3.2 Analysis of Secondary Efficacy Objective(s)

8.4.3.2.1 Statistical Hypotheses

Not applicable.

8.4.3.2.2 Analysis Sets

Not applicable.

8.4.3.2.3 Statistical Methods

Not applicable.

8.4.3.3 Analysis of Secondary Immunogenicity Objective(s)

8.4.3.3.1 Statistical Hypotheses

Not applicable.

8.4.3.3.2 Analysis Sets

FAS-2: Long term Immunogenicity Analysis Set.

8.4.3.3.3 Statistical Methods

Geometric Mean Concentration (GMC).

RVNA GMCs will be based on the logarithmically transformed (base10) values.

GMCs with the associated 95% confidence intervals (CIs) will be computed for each vaccine group at Year 3, 4, 5, 6, 7, 8, 9 and 10 by taking the exponential of the corresponding log-transformed (least squares) means and 95% confidence intervals, from an ANOVA model with fixed factors for group and center. Group differences along with

95%CIs will also be computed. Subjects will be included in this analysis until they receive the booster dose and they will be excluded thereafter.

Reverse Cumulative Distribution Plots.

The reverse cumulative distribution plots will be provided at Year 3, 4, 5, 6, 7, 8, 9 and 10 by treatment group.

Percentages of subjects with RVNA concentrations ≥ 0.5 IU/mL.

As a form of supplementary information, also percentage of subjects with RVNA concentrations ≥ 0.5 IU/mL, as measured by RFFIT assay at Year 3, 4, 5, 6, 7, 8, 9 and 10 will be presented in a tabular fashion.

